12.1.1. Efficacy Variables

Result of COVID-19 weekly nasopharyngeal (NP) test .

12.1.2. Safety Variables

The safety variables include results of vital sign measurements, adverse events, and serious adverse events.

12.2. Statistical Analyses

A statistical analysis plan (SAP) detailing the analyses will be developed prior to the database lock. All statistical analyses and data summaries will be performed using SAS® (Version 9.1 or higher) or other validated software. The SAP will serve as the final arbiter of all statistical analyses. Data will be summarized overall using descriptive statistics. Continuous data will be summarized with number of subjects (n), mean, median, minimum, maximum, relevant quartiles, standard deviation, coefficient of variation, and geometric mean (where applicable). Categorical data will be summarized using frequency counts and percentages. Chi Square or Fisher exact test will be used for comparing binary outcomes between treatment and control groups. Continuous variables will be compared between the study groups by means of two sample T test or Wilcoxon-rank-sum test.

12.2.1. Primary Analysis of Efficacy

All subjects who received at least one dose of study medication, will be used as the primary population for assessment of efficacy. The proportion of people whose NP sample becomes positive at least once during the trial will be compared between the study groups using Chi square or Fisher exact test. Survival analysis will be utilized to estimate the potential effects of hydroxychloroquine on COVID-19 free survival times. We will apply generalized linear mixed models to compare the positive conversion rate of COVID-19 between the study arms while controlling for other confounding factors. AIC and BIC criteria will be used to choose an appropriate covariance structure between the measurements collected at consecutive visits. An

interaction effect between time and study group will be added to the model to evaluate whether the relative risk of a positive conversion changes from visit to visit.

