9.1.5. Management of COVID-19 positive test

If the result of an NP swab test demonstrates the presence of SARS-CoV-2, the subject will be directed to immediately receive appropriate medical care and will discontinue study treatment and procedures, however the sponsor will continue to follow the subject until their condition is resolved or death. Patient management following a positive test during the study will not be directed by study procedures and will be at the discretion of the subject's physician.

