12. STATISTICS

12.1. Sample Size

A total sample of 360 individuals (180 in each arm) would provide at least 80% power to detect a relative risk reduction of 40% in the rate of positive NP samples when the anticipated rate of positive conversion among those taking hydroxychloroquine is approximately 30%.

The power calculation, which was based on Pearson Chi Square test, assumes the following:

- One-sided Type I error rate of 0.05
- Anticipated positive NP samples rate of 30% in the clinical arm
- A 40% lower risk of a positive NP sample comparing the hydroxychloroquine group vs the controls
- Loss to follow-up rate of 15%

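### The only confounder-adjusted model for conversion relies on a between-visit covariance that once-only conversion data barely inform; fitted as a subject random effect, it can inflate the group effect

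*Protocol*

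**What the plan says.** Protocol 7.3 lets qualified workers choose hydroxychloroquine or the control group. Protocol 12.2.1, repeated in SAP 6.1, plans three efficacy analyses:

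- an unadjusted chi-square or Fisher comparison of the proportion ever positive;
- a survival analysis, with no method or covariates named;
- a mixed model: "We will apply generalized linear mixed models to compare the positive conversion rate of COVID-19 between the study arms", with control for confounding.

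Only the third is said to adjust. Of its correlation structure the plan says: "AIC and BIC criteria will be used to choose an appropriate covariance structure between the measurements collected at consecutive visits". A time-by-group interaction is then added.

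Neither document states the link, how rows after a first positive are coded, whether the covariance is a random effect or a residual correlation, or whether a model with no covariance is among the candidates.

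On what follows a positive swab, Protocol 9.1.5 says the worker "will discontinue study treatment and procedures". Protocol 8.4.1 lists a positive test as a reason to stop drug and asks workers who stop drug to complete all visits and assessments if possible. Protocol 12.1.1 names the weekly swab result as the efficacy variable.

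**The concern.** A worker converts at most once. With rows ending at the first positive, each record is a string of negatives with at most one positive, always last. For any two visits of the same worker the earlier result is negative, so nothing is replicated from which a within-worker variance could be learned. Whatever value is fitted comes from the assumed form of the model.

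This matters because, in a random-intercept logistic model, the group odds ratio is conditional on the random effect and moves away from 1 as the fitted variance grows. A variance that drifts upward by chance can turn a moderate effect into a near-complete one, in the one planned estimate meant to deal with self-selection. Cutting the data at the first positive does not cure this.

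**Working it through.** **Inputs.** Protocol 12.1 gives 180 per arm and 15% loss, so 180 x 0.85 = 153 evaluable per arm. Protocol 7.1 gives 7 post-baseline visits. Protocol 12.1 also gives a relative risk of 0.60, "One-sided Type I error rate of 0.05" and "Anticipated positive NP samples rate of 30% in the clinical arm", which implies 30% / 0.60 = 50% in controls. I also ran 30% in controls against 18% on drug.

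**The plan's own figure.** With the pooled-variance two-proportion formula, one-sided 0.05 and 80% power, 30% vs 18% needs 156 per arm; 156 x 1.15 = 179.4, so 180. The rates as written (50% vs 30%) need 74 per arm, and power at 153 is 97.5%. So 180 is reproduced only if 30% is the control rate. Both pairs are carried below. The documents give no figure for the mixed model itself.

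**True effect per visit.** Assume a constant weekly risk h = 1 - (1 - p)^(1/7) and no real heterogeneity between workers. This gives h = 0.0943 (50%), 0.0497 (30%) and 0.0280 (18%). The visit-level odds ratios are 0.502 (50% vs 30%) and 0.550 (30% vs 18%).

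**How much the data say about the random-intercept SD.** Logit link, rows to first positive, expected data, SD held fixed and all else maximised:

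| SD | 50% vs 30%, visit-by-group interaction: deviance | Visit-1 OR | 30% vs 18%, no interaction: deviance | OR |
|---|---|---|---|---|
| 0 | 871.9471 | 0.50 | 616.42 | 0.55 |
| 1 | 871.9471 | 0.48 | 616.45 | 0.50 |
| 2 | 871.9471 | 0.40 | 616.56 | 0.39 |
| 3 | 871.9471 | 0.31 | 616.63 | 0.29 |
| 5 | 871.9471 | 0.17 | 616.69 | 0.15 |

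- With the interaction, each group has seven free visit parameters for seven conversion risks. Every SD reproduces the data exactly, so the likelihood is flat and the SD is not identified. The visit-7 OR slides from 0.50 to 0.06 over the same range.
- Without it, the deviance moves by 0.3 (30% vs 18%) or 0.8 (50% vs 30%) between SD 0 and 5, while the OR goes from 0.55 to 0.15 or from 0.50 to 0.08.
- With the interaction plus a balanced binary confounder (odds ratio 2), the deviance rises by only 0.87 (50% vs 30%) or 0.39 (30% vs 18%). The visit-1 OR moves from 0.49 to 0.16 or from 0.54 to 0.24.

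**Simulated trials, true SD 0, no interaction.** Share in which the mixed-model OR is less than half the fixed-effects OR (50% vs 30% / 30% vs 18%):

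| Setting | Random intercept always kept | AIC, no random effect allowed | BIC |
|---|---|---|---|
| Binary confounder, odds ratio 2 (800/758 trials) | 16% / 22% | not tabulated | not run |
| Same, confounder balanced (about 1,600 trials each) | 18% / 26% | 8% / 5% | random intercept chosen in 0.4% / 0.1% |
| No confounder | 29-30% in both | 8% / 2% | 0% / 0% |

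In the first setting AIC kept the random intercept in 9% and 5% of trials, and the median OR in those was 0.12.

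**Other readings of the text** (50% vs 30%; 30% vs 18% in brackets):

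- Marginal model, exchangeable correlation, rows to first positive: correlation about 0, OR 0.51 with or without it (50% vs 30% only, 40 trials).
- Zeros entered after conversion: SD goes to 0, OR 0.58 (0.59), no exaggeration.
- Positive carried forward to Day 49: SD runs to the fitting limit and the OR collapses to about 1e-11 (1e-9).
- Swabbing continues and positivity lasts 2 weeks (assumed): SD well estimated; OR 0.52 against 0.55 without the random effect (0.48 against 0.56).
- Swabbing continues and positivity lasts 3 weeks (assumed): OR 0.38 against 0.53 (0.34 against 0.55).

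**The case against.** The once-only structure is a reading, not something the plan states. Protocol 12.1.1 takes the weekly swab result as the variable, and 8.4.1 can be read as continuing swabs. Repeated results would then exist and the covariance could be estimated. This stands, with one limit: a second positive is not a second conversion, so that model describes being positive at a visit. Part of the shift at 3-week positivity is also the ordinary gap between subject-specific and population-averaged odds ratios.

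A covariance between measurements may mean a residual or marginal structure, which did not distort the OR when rows stopped at the first positive. This also stands. Against it, the plan names mixed models and likelihood criteria, so a random effect is a natural reading that nothing excludes.

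The selection rule may protect itself. It largely does if a model with no random effect is a candidate, and BIC then almost always rejects the spurious one. The plan does not say that it is a candidate, and under AIC a bad lower tail remains.

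A reader might infer that the covariance can never be estimated, that the treatment effect will be grossly exaggerated, or that AIC/BIC selection is meaningless here. The documents support none of these without conditions. The first is exact only for the categorical interaction without covariates or for degenerate coding. The second needs a retained random effect or carried-forward positives. The third fails once the no-random-effect model is allowed.

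Finally, the planned survival analysis could meet the need if it named its method and covariates.

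**Conclusion.** The concern holds conditionally. For once-only conversion with rows ending at the first positive, a subject random-effect variance is unidentified or nearly so, and the only estimate with stated confounder control depends on it. A retained random intercept more than halves the OR, relative to the fixed-effects value, in roughly 16-30% of simulated trials. With a no-random-effect candidate the share is about 2-8% under AIC and about 0% under BIC. A marginal covariance does little harm.

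These figures assume a logit link, constant weekly risk, no true heterogeneity and 153 per arm. A log link was not examined, although 12.2.1 speaks of relative risk. The chi-square/Fisher comparison is untouched. This should be corrected, but confidence is medium because the coding, the type of covariance and swabbing after a positive are all left open.

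**What to change.** 1. Reconcile Protocol 8.4.1 and 9.1.5 on whether swabbing continues after a positive, and carry the answer into the SAP.
2. For the conversion outcome, in Protocol 12.2.1 and SAP 6.1, replace the mixed model by a confounder-adjusted discrete-time hazard model. Use one record per worker per visit up to and including the first positive, with visit indicators, group and named confounders. Include no subject random effect or within-worker covariance, and use robust standard errors. State the link.
3. Keep the planned time-by-group term as a separate evaluation within this model.
4. Delete the AIC/BIC covariance sentence for this outcome.
5. Report the adjusted Day 49 risk ratio by standardisation: for each worker compute 1 minus the product of (1 - fitted visit risk) under each group, average over all workers, and take the ratio.

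On the simulated once-only data without confounders, the hazard model recovered the truth: median OR 0.50 (10th-90th percentile 0.38-0.64) for a true 0.502, and 0.54 (0.39-0.75) for a true 0.550.

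The cost is wording in two documents and no new data. The planned covariance selection and any subject-specific reading of the odds ratio are given up.

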13. DIRECT ACCESS TO SOURCE DATA/DOCUMENTS

13.1. Audits and Inspections

Principal investigators and institutions involved in the study will permit study-related monitoring, audits, and IRB/EC review, and regulatory inspections, by providing direct access to all study records. In the event of an audit, the principal investigator agrees to allow the Sponsor, representatives of the Sponsor, the US Food and Drug Administration (FDA), and other relevant regulatory authorities access to all study records.

The principal investigator should promptly notify the Sponsor or designee of any audits scheduled by any regulatory authorities and promptly forward copies of any audit reports received to the Sponsor or designee.

14. QUALITY CONTROL AND QUALITY ASSURANCE

14.1. Quality Assurance

To ensure compliance with Good Clinical Practices and all applicable regulatory requirements, BSWRI may conduct a quality assurance audit of the investigator's clinical site, including CTM/IMP storage facilities.

14.2. Financial Disclosure

Principal investigators and sub-investigators are required to provide financial disclosure information prior to starting the study. In addition, the principal investigator and sub-investigators must provide the Sponsor or designee with updated information, if any relevant changes occur during the course of the investigation and for one year following the completion of the study.

No potential investigator who has a vested financial interest in the success of this study may participate in this study.

14.3. Sponsor Obligations

The Sponsor or designee is not financially responsible for further testing/treatment of any medical condition that may be detected during the Screening process. In addition, in the absence of specific arrangements, the Sponsor or designee is not financially responsible for treatment of the subject's underlying disease.

14.4. Investigator Documentation

Before beginning the study, the principal investigator will be asked to comply with ICH E6(R1) 8.2 and Title 21 of the Code of Federal Regulations (CFR) by providing the essential documents to the Sponsor or designee, which include but are not limited to the following:

- An original investigator-signed investigator agreement page of the protocol;
- The IRB/EC approval of the protocol;
- The IRB- or EC-approved informed consent, samples of site advertisements for recruitment for this study, and any other written information regarding this study that is to be provided to the subject or legal guardians;
- A Form FDA 1572, fully executed, and all updates on a new fully executed Form FDA 1572;
- Curricula vitae for the principal investigator and each sub-investigator listed on Form FDA 1572. A curricula vitae and current licensure, as applicable, must be provided. The curricula vitae must have been signed and dated by the principal investigators and sub-investigators within 2 years before study start-up to indicate the documents are accurate and current;
- Completed financial disclosure forms ([Section 14.2](#)) to allow the Sponsor or designee to submit complete and accurate certification or disclosure statements required under US Title 21 CFR 54. In addition, the investigators must provide to the Sponsor or

designee a commitment to update this information promptly if any relevant changes occur during the course of the investigation and for 1 year following the completion of the study;

- Laboratory certifications and normal ranges for any laboratories used by the site for the conduct of this study.

14.5. Clinical Study Insurance

In accordance with the respective national drug laws, the Sponsor has taken out subject liability insurance for all subjects who give their consent and enroll in this study. This insurance covers potential fatalities, physical injuries, or damage to health that may occur during the clinical study.

14.6. Use of Information

All information regarding hydroxychloroquine supplied by the Sponsor to the investigator is privileged and confidential. The investigator agrees to use this information to accomplish the study and will not use it for other purposes without consent from the Sponsor. Furthermore, the investigator is obligated to provide the Sponsor with complete data obtained during the study. The information obtained from the clinical study will be used towards the development of hydroxychloroquine/azithromycin and may be disclosed to regulatory authorities, other investigators, corporate partners, or consultants as required.

15. ETHICS

15.1. Institutional Review Board (IRB) or Ethics Committee Review

The protocol and the proposed informed consent form must be reviewed and approved by a properly constituted IRB/EC before study start. Each investigator must provide the Sponsor or its designee a signed and dated statement that the protocol and informed consent have been approved by the IRB/EC for that site before consenting subjects. Prior to study initiation, the investigator is required to sign a protocol signature page confirming agreement to conduct the study in accordance with this protocol and to give access to all relevant data and records to the Sponsor, its designee, and regulatory authorities as required.

The IRB/EC chairperson or designee must sign all IRB/EC approvals and must identify the IRB/EC by name and address, the clinical protocol, and the date approval and/or favorable opinion was granted.

The principal investigator is responsible for obtaining reviews of the clinical research at intervals specified by the IRB/EC, but not exceeding 1 year. The principal investigator must supply the Sponsor or designee with written documentation of reviews of the clinical research.

15.2. Ethical Conduct of the Study

This clinical study was designed and shall be implemented and reported in accordance with the ICH Harmonized Tripartite Guidelines for Good Clinical Practice, with applicable local regulations (e.g., US Code of Federal Regulations Title 21, European Directive 2001/20/EC), and with the ethical principles laid down in the Declaration of Helsinki.

The principal investigator agrees to conduct the study in accordance with the International Conference on Harmonization (ICH) for Guidance for Industry on Good Clinical Practice (GCP) ICH E6(R1)

[http://www.ich.org/fileadmin/Public_Web_Site/ICH_Products/Guidelines/Efficacy/E6/E6_R1_Guideline.pdf] and the principles of the Declaration of Helsinki

[<http://www.wma.net/en/30publications/10policies/b3/>]. The principal investigator must conduct all aspects of this study in accordance with all national, state, and local laws or regulations.

15.3. Written Informed Consent

Because the study will be conducted under a United States Investigational New Drug Application, a signed informed consent form, in compliance with Title 21 of the United States Code of Federal Regulations (CFR) Part 50, will be obtained from each subject before the subject enters the study. For sites outside of the United States, the signed consent will be obtained in accord with local regulations, ICH E6 (R1), and principles of the Declaration of Helsinki. An informed consent template may be provided by the Sponsor or designee to the investigators. The consent must be reviewed by the Sponsor or designee before IRB/EC submission. Once reviewed, the consent will be submitted by the principal investigator to his or her IRB/EC for review and approval before the start of the study. If the informed consent form is revised during the course of the study, all participants affected by the revision must sign the revised IRB/EC-approved consent form.

Before enrollment, each prospective subject will be given a full explanation of the study and be allowed to read the approved informed consent form. Once the principal investigator or designee is assured that the subject understands the implications of participating in the study, the subject will be asked to give consent to participate in the study by signing the informed consent form.

Eligible subjects may only be included in the study after providing written (witnessed, where required by law or regulation), IRB/EC-approved informed consent. Informed consent must be obtained before conducting any study-specific procedures (*i.e.*, all of the procedures described in the protocol). The process of obtaining informed consent must be documented in the subject source documents.

Any changes to the proposed consent form suggested by the investigator must be agreed to by the Sponsor before submission to the IRB/EC, and a copy of the approved version and the notice of approval must be provided to the Sponsor's designated monitor after IRB/EC approval.

The principal investigator or designee will provide a copy of the informed consent form (signed copy to be provided per applicable law) to the subject and/or legal guardian. The original form will be maintained in the subject's medical records at the site.

15.4. Confidentiality

All laboratory specimens, evaluation forms, reports, and other records will be identified in a manner designed to maintain participant confidentiality. All records will be kept in a secure storage area with limited access. Clinical information will not be released without the written permission of the subject (or the subject's guardian), except as necessary for monitoring and auditing by the Sponsor, its designee, the FDA or applicable regulatory authorities, or the IRB/EC.

The principal investigator and all employees and coworkers involved with this study may not disclose or use for any purpose other than performance of the study, any data, record, or other unpublished confidential information disclosed to them for the purpose of the study. Prior written agreement from the Sponsor or designee must be obtained for the disclosure of any said confidential information to other parties.

15.5. Modification of the Protocol

Any changes that arise after the approval of the protocol must be documented as protocol amendments. The FDA or other applicable regulatory agencies must be notified of protocol amendments. The changes will become effective only after approval of the Sponsor, the investigator, the IRB/EC, and where necessary, the applicable regulatory agency. In cases when the protocol is modified to enhance subject safety, changes may be implemented and the amendment must be immediately submitted to the IRB/EC.

The investigator is responsible for informing the IRB/EC of all problems involving risks to subjects according to national legislation. In case of urgent safety measures, the Sponsor will immediately notify the investigators and relevant regulatory agencies, including FDA in accord with 21 CFR 312.32.

15.6. Protocol Deviations

The principal investigator or designee must document any protocol deviation. The IRB/EC must be notified of all protocol deviations in a timely manner by the principal investigator or designee as appropriate. Protocol deviations will be documented by the responsible monitor during monitoring visits, and those observations will be communicated to the investigator.

If there is an immediate hazard to a subject the principal investigator may deviate from the protocol without prior Sponsor and IRB/EC approval. The Sponsor and IRB/EC must be notified of the deviation.

